Measurements & procedures	
Two stool samples will be collected if possible on two consecutive days or otherwise within a maximum of 5 days apart. The medical history of the participating individuals will be assessed with a standardized questionnaire, in addition to a clinical examination carried out by the study physician on the treatment day.
 
Randomization of participants into the two treatment arms will be stratified according to intensity of infection. Participants will be interviewed before treatment for clinical symptoms and 3 hours after every morning treatment and 24 hours after every morning treatment about the occurrence of adverse events. The efficacy of the treatment will be determined 14-21 days post-treatment by collecting another two stool samples. All stool samples will be examined with duplicated Kato-Katz thick smears.

Statistical Analyses	
The primary analysis will include all participants with primary end point data (available case analysis). Supplementary, two sensitivity analyses will be conducted imputing all missing endpoint data as treatment failures or all as treatment success. CRs will be calculated as the percentage of egg-positive participants at baseline who become egg-negative after treatment. CRs will be compared by using unadjusted logistic regression. To assess model robustness with respect to covariates, adjusted logistic regressions (adjustment for age, sex, school, weight and strata) will be performed.
 
Geometric and arithmetic mean egg counts will be calculated for the different treatment arms before and after treatment to assess the corresponding ERRs. Bootstrap resampling method with 5,000 replicates will be used to calculate 95% confidence intervals (CIs) for ERRs and the difference of the ERRs.

GCP statement	This study will be conducted in compliance with the protocol, the current version of the Declaration of Helsinki, ICH-GCP E6 as well as all national legal and regulatory requirements.
Key explanation for the inclusion of	This study will be carried out in individuals aged 6-12 years old, since an infection with hookworm and other soil-transmitted

participants	helminths occurs most often in this age group.
Recruitment procedure	The study will be carried out in primary schools in Pemba Island, Tanzania.
Coverage of damages	Winterthur Police Nr. 4746321, National Insurance Cooperation of Tanzania LTD, GTA No: 00062.

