The primary objective of the study is to assess the CR (*i.e.* conversion from being egg positive pre-treatment to egg negative post-treatment) of two different mebendazole regimens against hookworm in children (6 - 12 years old): (i) 100 mg of mebendazole twice a day for 3 days and (ii) 500 mg of mebendazole single dose. Thus, the **primary endpoint** of the study is the CR of these two regimens of mebendazole against hookworm.

Additional **secondary endpoints** are (1) the ERR of these two regimens against hookworm, (2) the CR and ERRs of both mebendazole regimens against concomitant soil-transmitted helminth infections, and (3) the safety of both mebendazole regimens. **Exploratory endpoints** include comparison of the sensitivity of Kato Katz to quantitative polymerase chain reaction assays, prevalence of genetic resistance markers among participants, and distribution of hookworm species among participants.

4. Methodology

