4.2 Trial design

4.2.1 Baseline survey and screening

This trial will take place in the two primary schools (Bagamoyo School and Piki School) in Pemba, Tanzania, which have been found to have a high prevalence of hookworm in previous studies. Among those children for whom informed consent is obtained, each participant will receive an empty container at school, which they return the following day with a stool sample. Stool samples will be collected and transported by car to the central laboratory. Two stool samples will be collected from each participating individual on different days, to adequately cover the egg shedding cycle of 24-48 hours, until a total of 180 hookworm-infected participants have been identified, preferable with *A. lumbricoides* and/or *T. trichiura* co-infections (Fig. 1). The prevalence for hookworm infected individuals is expected to be between 20% and 40% [17, 49, 50], hence we anticipate screening around 500-1,000 individuals to reach the total number of participants. The number of screened individuals will depend on the prevalence of the parasite.

The Kato-Katz technique will be used for the quantitative assessment of STH infections. Two stool samples will be collected from each participant before treatment and from each sample

duplicate Kato-Katz thick smears (41.7 mg each) will be prepared [51]. The slides will be analysed under a microscope by experienced technicians and a subsequent independent quality control of sample results (10%) will be conducted. Results are considered correct if the following tolerance margin is not exceeded: (i) No difference in presence/absence of hookworm, *A. lumbricoides* and *T. trichiura*, (ii) Egg counts are ± 10 eggs for counts ≤ 100 eggs or $\pm 20\%$ for counts > 100 eggs (for each species separately) [52]. In case discrepancies above the tolerance margin are noted in one or more slides, all slides are re-read by the local technicians. The new results are discussed, so that in case of discordant results, slides can be re-evaluated to reach consensus. Infection intensity expressed as the arithmetic and geometric mean egg count per gram of stool (EPG) will be calculated for each treatment arm.

[figure not shown]

Figure 1: Mebendazole efficacy study-flow.

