4.3. Measure to minimize bias

Study participants eligible for treatment will be randomly assigned to one of the two treatment arms using a computer-generated stratified block randomization code. The random allocation sequence with varying random blocks of four or eight and stratified by 2 levels of baseline infection intensity (light: 1-1999 EPG, and moderate plus heavy: ≥ 2000 EPG hookworm infections) will be provided by a statistician. Both treatment arms will have an equal number of participants with light infection intensity, although the number of light versus moderate/heavy infections are not expected to be equal in each arm, depending on the distribution of infection intensity in the recruited cohort. The codes will be held in a locked cabinet at the Swiss Tropical and Public Health Institute. A copy of this code will be kept in a sealed envelope by one of the co-investigators (will only be unblinded in case there is a serious adverse event, determined by the principal investigator upon consultation with the co-investigators). The blinding will be maintained throughout the trial until data entry and processing are complete and the data have been verified. Following release of the final data, the randomization codes will be released.

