7.3. Description of statistical methods

The primary available case analysis will include all participants with primary end point data. In addition, an intention-to-treat analysis will be conducted considering all participants with missing endpoint data as treatment failure or all as treatment success to ensure that the results are not sensitive to potential loss to follow-up bias. CRs will be calculated as the percentage of egg-positive children at baseline who become egg-negative after treatment. EPG will be assessed by adding up the egg counts from the quadruplicate Kato-Katz thick smears and multiplying this number by a factor of six. The ERR will be calculated as:

$$ERR = 1 - \frac{\frac{1}{n} e^{\sum \log(EPG_{follow-up} + 1)} - 1}{\frac{1}{n} e^{\sum \log(EPG_{baseline} + 1)} - 1}$$

In the primary model we estimate the difference among CRs by using unadjusted logistic regressions. In a subsequent analysis an adjusted logistic regression (adjustment for age, sex, school, weight and strata) will be performed.

Geometric mean egg counts will be calculated for the different treatment arms before and after treatment to assess the corresponding ERRs. Bootstrap resampling method with 5,000 replicates will be used to calculate 95% confidence intervals (CIs) for ERRs and the difference between the ERRs.

Adverse events will be evaluated descriptively as the difference of proportion reporting adverse events before and after treatment.

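### The adjusted cure-rate model carries only the hookworm stratum for infection intensity; for the secondary co-infection cure rates it should also carry the species' own baseline egg count

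*Combined protocol and SAP*

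**What the plan says.** The main cure-rate comparison is unadjusted. Section 7.3 states: "In the primary model we estimate the difference among CRs by using unadjusted logistic regressions". It then adds the adjusted model: "In a subsequent analysis an adjusted logistic regression (adjustment for age, sex, school, weight and strata) will be performed". The synopsis gives that second model its purpose: "To assess model robustness with respect to covariates, adjusted logistic regressions (adjustment for age, sex, school, weight and strata) will be performed".

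Section 4.3 defines the strata by hookworm egg count alone: "light: 1-1999 EPG, and moderate plus heavy", the upper level being "moderate plus heavy: ≥ 2000 EPG hookworm infections". Section 7.1 justifies this by noting that hookworm cure may depend on infection intensity.

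Section 3 lists among the secondary endpoints "the CR and ERRs of both mebendazole regimens against concomitant soil-transmitted helminth infections". Neither 7.3 nor the synopsis gives a separate model for these.

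The baseline counts exist. Section 4.2.1 says "The Kato-Katz technique will be used for the quantitative assessment of STH infections", with two samples and duplicate smears per child, and its slide quality-control rule is applied "for each species separately".

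**The concern.** For hookworm, the plan both stratifies on intensity and adjusts for the stratum. For T. trichiura and A. lumbricoides it does neither with the relevant count. The stratum measures a different worm, and the co-infected children are a subset on which randomisation was not stratified by the species analysed.

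Cure in 7.3 means going from egg-positive to egg-negative, judged on four slides, so a heavier starting burden should make cure harder to reach. If so, the own-species count is the most plausible predictor of cure, and a robustness check that leaves it out cannot show whether the regimen comparison is robust to it. At stake is how the co-infection comparison is interpreted if the arms happen to differ in burden.

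**Working it through.** **The plan's own figure.** Section 7.2 sizes the trial on hookworm: cure 20% vs 40%, 80% power, two-sided 5%. With unpooled variance, n = (1.960 + 0.842)² × (0.20×0.80 + 0.40×0.60) / 0.20² = 7.849 × 0.40 / 0.04 = 78.5, so 79 per arm, as stated. No figure is given for T. trichiura.

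**Why the count should predict cure (illustration).** EPG is the four-slide total times six (7.3), so 30 EPG is 5 eggs and 300 EPG is 50 eggs. Assume an 80% egg reduction and Poisson counts. The expected follow-up totals are 1 and 10 eggs, and the chance of seeing none is e⁻¹ = 37% against e⁻¹⁰, below 0.01%. With a 90% reduction the pair is 61% vs 0.7%; with 50% it is 8% vs about 0%. Real counts are noisier, but the direction is clear.

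**Assumptions for size.** The documents give no co-infected number, T. trichiura cure rate or prognostic strength. Assumed: 45 or 79 co-infected per arm; cure 10% vs 25% or 20% vs 40%; cure odds ratio per SD of log baseline count of 1.0 (not prognostic), 0.70, 0.50 or 0.35.

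**Chance imbalance.** The 95% range for the arm difference in mean log count is ±1.96 × √(2/n) SD:
- 45 per arm: ±0.41 SD
- 79 per arm: ±0.31 SD

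The shift in the regimen odds ratio is about (odds ratio per SD) raised to minus that difference:

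| Cure OR per SD | 45 per arm | 79 per arm |
|---|---|---|
| 0.70 | 1.16 | 1.12 |
| 0.50 | 1.33 | 1.24 |
| 0.35 | 1.54 | 1.39 |

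**Power.** 3,000 simulated trials per scenario, Wald test at two-sided 5%. Further assumptions: correlation 0.2 between the own-species count and the latent hookworm intensity behind the stratum, and the other listed covariates not prognostic. Each cell shows the planned adjusted model → the same model plus own-species log EPG, in %:

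| Cure OR per SD | 20% vs 40%, 79/arm | 20% vs 40%, 45/arm | 10% vs 25%, 79/arm | 10% vs 25%, 45/arm |
|---|---|---|---|---|
| 1.0 | 79.0 → 78.8 | 54.0 → 54.0 | 68.2 → 68.8 | 44.5 → 44.7 |
| 0.70 | 79.2 → 80.5 | 54.1 → 54.5 | 69.1 → 70.5 | 44.4 → 45.2 |
| 0.50 | 77.8 → 81.6 | 55.6 → 59.0 | 69.0 → 72.9 | 43.6 → 46.0 |
| 0.35 | 77.7 → 83.7 | 53.1 → 60.0 | 68.5 → 74.8 | 42.4 → 46.7 |

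The gain is nil when the count is not prognostic, up to about 1 point at 0.70, 2 to 4 at 0.50 and 4 to 7 at 0.35. A still steeper relation would give more: at 0.25 per SD, a smaller model with only treatment and stratum gained 7 to 10 points.

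**Power when the imbalance is unfavourable.** Take 20% vs 40%, 79 per arm, odds ratio 0.50 per SD, and only trials where the better arm is more than 1 SE heavier at baseline. Power is 64% in the planned adjusted model and 82% with the count added.

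**Type I error** (20% in both arms): 4.7–5.6% in the planned adjusted model and 4.7–5.9% with the count added.

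**The case against.** Several points on the other side stand.

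- **The co-infection model is inferred.** The regressions in 7.3 follow the primary available-case analysis, and the primary endpoint is hookworm, for which the hookworm stratum is the right intensity term. No passage states a between-arm T. trichiura test. At minimum, then, the co-infection model is unspecified, which is itself a reason to name it.
- **The adjusted model is a robustness check.** Changing its covariates adds no power to the unadjusted comparison.
- **The intensity remark in 7.1 concerns hookworm.** The case for T. trichiura rests on how cure is defined, not on that sentence.
- **The gain is not one of precision.** In logistic regression, adding a prognostic covariate moves the target to a larger conditional odds ratio while its standard error rises. In one scenario (70 per arm, 20% vs 40%, odds ratio 0.41 per SD) the median standard error went from 0.389 to 0.424 while power went from 74.0% to 79.8%.
- **Chance imbalance is not bias.** Randomisation balances the count in expectation, and the 5% error rate already allows for imbalance. Baseline EPG means by arm are planned, so an imbalance would be visible. But seeing it is not adjusting for it, and a covariate added after seeing it would be a post hoc choice.

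A reader might infer that the plan throws away substantial power at no cost, or that the hookworm stratum should be replaced. The documents support neither. They give nothing from which a T. trichiura power loss could be computed, and the stratum is part of the randomisation, so it belongs in the model.

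**Conclusion.** The point holds as a minor improvement to a secondary endpoint. The only covariate list omits a baseline value that is collected anyway and that probably matters for the species analysed. The main benefit is protection against chance imbalance: a shift of the regimen odds ratio by a factor of up to about 1.24 to 1.33 at an assumed odds ratio of 0.50 per SD, less if the count is weakly prognostic, none if it is not.

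The power gain is about 0 to 7 points over assumed odds ratios from 1.0 to 0.35 per SD, and only in the adjusted model. All these sizes depend on assumed co-infection numbers, cure rates and prognostic strength. The hookworm primary endpoint and its sample size are unaffected.

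**What to change.** Add to 7.3, before the randomisation codes are released: for each co-infection cure rate, the adjusted logistic regression contains the listed covariates, including the stratum, plus log baseline EPG of the species analysed, and it is pre-specified alongside the unadjusted model. The logarithm is always defined, because only children egg-positive for that species enter the analysis (one egg on four slides is 6 EPG).

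Add a rule for sparse data, applied to counts pooled over arms. If cures or failures are too few for the full list, keep own-species log EPG and the stratum and drop the other covariates, or use Firth-penalised logistic regression. This could arise for T. trichiura, where 45 per arm at 10% vs 25% gives 45 × 0.35 ≈ 16 cures for eight coefficients including the intercept. It could also arise for A. lumbricoides, where section 2 reports excellent cure rates, so failures may be few.

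The cost is a few lines of text and no new data. The downsides are one more coefficient and an adjusted odds ratio conditional on one more covariate, which should be said when it is reported next to the unadjusted one.

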5.2 Inclusion criteria

1. Written informed consent signed by parents and/or caregiver; and oral assent by participant.
2. Able and willing to be examined by a study physician at the beginning of the study.
3. Able and willing to provide two stool samples at the beginning (baseline) and approximately three weeks after treatment (follow-up).

4. Positive for hookworm eggs in the stool (≥ 100 EPG and at least two Kato-Katz thick smears slides with more than one hookworm egg).
5. Absence of major systemic illnesses, e.g. diabetes, severe anemia (HB<8.0 g/l) as assessed by a medical doctor at school, upon initial clinical assessment.
6. No known or reported history of chronic illness as cancer, diabetes, chronic heart, liver or renal disease.
7. No recent anthelmintic treatment (within past 4 weeks).
8. No known allergy to study medications (mebendazole and albendazole).

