5.3. Exclusion criteria

1. No written informed consent by parents and/or caregiver; no oral assent by participant.
2. Menarche, based on self-report
3. Presence of major systemic illnesses, e.g. diabetes, severe anemia (HB<8.0 g/l) as assessed by a medical doctor, upon initial clinical assessment.
4. History of acute or severe chronic disease.
5. Recent use of anthelmintic drug (within past 4 weeks).
6. Attending other clinical trials during the study.
7. Negative diagnostic result for hookworm eggs in the stool (< 100 EPG (total of the four slides) and/or only one Kato-Katz thick smear slide with more than one hookworm egg).

Participants who were diagnosed with a STH infection, but who were excluded from the study due to one or several of the above-mentioned exclusion criteria, including withdrawals, will be offered standard anthelmintic treatment (albendazole).

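### The four slides that admit a child at 100 EPG or more are also the hookworm ERR baseline, so regression to the mean raises both arms' ERRs and shrinks their difference by a common but unknown factor

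*Combined protocol and SAP*

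**What the plan says.** - **Selection.** Section 5.2 admits a child who is "Positive for hookworm eggs in the stool (≥ 100 EPG and at least two Kato-Katz thick smears slides with more than one hookworm egg". Section 5.3 mirrors this by excluding a "Negative diagnostic result for hookworm eggs in the stool (< 100 EPG (total of the four slides", so the rule is applied to the pooled four slides.
- **Sampling.** Section 4.2.1: "Two stool samples will be collected from each participant before treatment and from each sample" duplicate smears are made, which gives the four slides. Neither the visit table in section 4.5 nor Appendix 2 shows another stool between screening and treatment.
- **Measure.** Section 7.3: "EPG will be assessed by adding up the egg counts from the quadruplicate Kato-Katz thick smears" and multiplying by six.
- **Estimates.** Section 7.3: "Geometric mean egg counts will be calculated for the different treatment arms before and after treatment to assess the corresponding ERRs". Bootstrap 95% intervals are planned for each ERR and for the difference between them.
- **Status.** The Synopsis lists the geometric-mean ERR against hookworm first among the secondary endpoints. Covariate and stratum adjustment is planned only for the cure-rate logistic model. Regression to the mean is not mentioned.

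**The concern.** A four-slide count is a noisy reading of a child's usual egg output. An entry threshold on that reading favours children caught on a high day. Their counts would fall on re-examination without any drug, and the follow-up stools are not selected on their result. Both arms receive mebendazole, so no untreated arm shows how large that fall is.

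Two things are at stake. Section 3 hypothesises that both regimens are effective, and each arm's ERR will overstate that effect. The difference between ERRs, which bears on the secondary objective of superiority, will understate the advantage of the better regimen. Randomisation makes the inflation equal in the two arms in expectation, but a common inflated denominator does not cancel from a difference of ERRs.

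**Working it through.** **The plan's own figure.** The only power figure is 79 per arm (section 7.2), for cure rates of 20% and 40%, two-sided 5%, 80% power. With unpooled variance: (1.960 + 0.842)² × (0.2×0.8 + 0.4×0.6) / 0.2² = 7.849 × 0.40 / 0.04 = 78.49, rounded up to 79. It reproduces, and it uses no egg count.

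**Direction.** Let B be the baseline geometric mean that fresh slides would give in the enrolled children, K·B the mean on the selecting slides (K > 1), and F₁ and F₃ the follow-up means for single dose and 3-day.

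- Observed ERR in an arm = 1 − F/(K·B). Its upward bias is (F/B)(1 − 1/K), larger where F is larger, that is, in the weaker arm.
- Observed difference = (F₁ − F₃)/(K·B) = true difference / K.
- The ratio F₃/F₁ contains neither B nor K.

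**Size.** The documents do not allow K to be computed. It was simulated with 600,000 children per scenario, applying the section 5.2 rule to four slides with EPG = 6 × eggs. Assumptions, none from the documents:

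- 60-90% truly infected; log-normal EPG with median 100-800 and log-SD 1.0-1.5;
- day-to-day log-SD 0.3-0.9; negative-binomial slides with dispersion 5 to 1;
- cure 20% and 40% (section 7.2), with egg output in uncured children multiplied by 0.5 (single dose) and 0.35 (3-day).

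Section 4.2.1 expects a prevalence of 20-40% and uses it as a qualifying share: 180/0.40 = 450 and 180/0.20 = 900, against a stated 500-1,000 to screen. Among scenarios in which 20-40% qualify:

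| | Mildest | Strongest |
|---|---|---|
| K | 1.09 | 1.89 |
| Single-dose ERR, fresh → reused baseline | 82.2% → 83.7% | 79.7% → 89.2% |
| 3-day ERR, fresh → reused baseline | 95.0% → 95.4% | 93.5% → 96.5% |
| Difference (points) | 12.8 → 11.7 | 13.8 → 7.3 |
| Shrinkage, 1 − 1/K | 8% | 47% |

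The single-dose ERR is therefore raised by 1.5 to 9.5 points and the 3-day ERR by 0.4 to 3.0. The follow-up ratio does not move beyond rounding: mildest 0.050/0.178 = 0.28 and 0.046/0.163 = 0.28; strongest 0.065/0.203 = 0.32 and 0.035/0.108 = 0.32.

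Over the whole grid K ran from 1.01 to 1.89. The low end (shrinkage 1 − 1/1.01 = 1%) needs a median of 800 EPG and low noise, and there 58-87% of screened children qualify.

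**Cross-checks.** A different model (gamma variation between stools, 17-48% qualifying) gave shrinkage of 16-47%. Appendix 2 takes a second stool only from children positive on the first; adding that rule left K essentially unchanged. The simulations used the geometric mean named in the text of 7.3, not the formula as printed.

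**The case against.** **Intensity may be well above the threshold.** Section 2 puts recent hookworm prevalence on Pemba at 36-97%, citing the same sources as the 20-40% in section 4.2.1. Section 4.2.1 itself calls prevalence in these schools high, and section 4.3 stratifies at 2000 EPG. In low-intensity models that give the larger K, only 0.3-6.6% of enrolled children reach 2000 EPG, about 1 to 12 of 180, which leaves that stratum nearly empty. Higher-intensity runs with 74-92% qualifying gave K of 1.03-1.25. This stands: the documents do not say which setting applies, and the bias could be trivial.

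**Inference is barely touched.** A common K scales the ERR difference and, to first order, its standard error together. Sign and significance are essentially unchanged, and no ERR test or decision rule is planned. This stands too. What is distorted is the size of secondary point estimates.

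**Stronger readings that a reader might infer.**

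- *That the regimen comparison is invalid or the trial underpowered.* The powered comparison is cure rate by logistic regression, which has no baseline count as denominator.
- *That ERRs are overstated by the full no-drug figure, about 8-47% in the 20-40% scenarios.* That is what an untreated arm would show, and there is none. With the assumed drug effects the inflation is the smaller number of points given above.
- *That the follow-up ratio gains precision.* Any larger z-value in simulation reflects the change of scale and cannot be credited to removing the bias.

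The arithmetic-mean ERR, also in the Synopsis, is less affected (no-drug value about 1.5-22%), but the endpoint is defined on geometric means.

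**Conclusion.** The point holds as a cheap improvement. That the selecting slides are also the ERR baseline follows from the text, and the direction follows from algebra: both geometric-mean ERRs are raised, the weaker arm's most, and their difference is divided by a common K.

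The size is an assumption: about 8-47% shrinkage if 20-40% of screened children qualify, and as little as about 1% if typical intensity is far above 100 EPG with little day and slide noise. A true null stays null. The planned cure-rate comparison and the 79 per arm are not affected. Nothing elsewhere in the plan corrects the effect.

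**What to change.** In section 7.3:

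1. Report the between-arm egg-count contrast as the ratio of follow-up hookworm geometric means, 3-day over single dose, with a 95% interval from the bootstrap already planned. It may be adjusted for the randomisation stratum.
2. Keep each arm's ERR and the difference between ERRs as descriptive results, with a statement that they include regression to the mean from the 100 EPG entry threshold.

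**Cost.** A few lines of SAP wording and one more estimate, on a scale less familiar to readers than the ERR. No new stools are needed.

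**Not recommended as things stand:** a baseline from the second stool only, in children whose first stool alone meets the rule (17 eggs × 6 = 102 EPG, both slides above one egg). Under section 5.2 the second stool would not then affect entry. Appendix 2, however, accumulates its enrolment total from second-stool positives. When a positive second stool was required in simulation, the no-drug ERR of this subset rose to as much as about 25%. Section 5.2 and Appendix 2 would first have to be reconciled so that enrolment does not depend on the second stool. A two-slide EPG would also need a factor of 12 (1000 / (2 × 41.7) ≈ 12), not the factor of six in 7.3.
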